8.3. Statistical analysis for dose proportionality – Single and Repeat dose study parts

8.3.1. Endpoints/Variables

To assess the dose proportionality, the statistical analysis will be based on AUC, Cmax and Ctau variables, as appropriate in the single and repeat dose study part.

8.3.2. Summary Measure

The summary measure will be the point estimates and 90% CIs of mean slopes of $\log_e(\text{dose})$ in the single and repeat dose study part.

8.3.3. Population of Interest

These analyses will be based on the PK population.

8.3.4. Strategy for Intercurrent (Post-Randomization) Events

In the Table 4 below, the possible intercurrent events and the rationale for relating them to treatment or otherwise is described. Once a subject discontinues from study treatment, they will proceed straight to follow up and no further data will be collected.

All subjects' data will be included in data listings irrespective of the strategies followed for the analysis.

If feasible, subjects will be replaced until the desired sample size is attained.

Table 4 Strategies for Intercurrent events

Intercurrent events	Relation to treatment and rationale	Strategy, rationale and details of action taken
Subject withdraws study consent	
Not related to treatment/
 
Subject drops out due to logistic reasons and not due to any event related to treatment
	
 - The strategy will be a While-on-Treatment strategy, where we are interested in the treatment effects prior to the withdrawal only. - Subjects' data available up to the withdrawal will be included in the dose proportionality analyses. - If a subject withdraws consent during a period, the missing data post withdrawal will not be imputed. - The derived PK parameters for e.g., AUC, C_{max} etc. of that partially completed period will be calculated if data permits (See section

		8.1.1.2 Derived Pharmacokinetic Parameters for details on derivation criteria).
Subject does not take the full treatment	
Not related to treatment/
 
The treatment will be administered as a powder dissolved in diluent. To ensure all treatment is ingested, the bottle containing the dispersion will be rinsed three times and the subject will be expected to ingest this in addition to the initial dispersion. If three rinses are not all ingested, the subject may not take the full treatment dose.
	
In the current formulation, it is hard to measure the exact proportion of dose ingested if not all rinses are taken. It is also uncertain whether the formulation could change in future development. To account for this, we propose two different strategies described below. If this intercurrent event is not observed, then both strategies will provide the same results and only the hypothetical strategy will be presented for the final analysis.
 
Primary analysis
 
 - The strategy will be a Hypothetical strategy, where we are interested in the treatment effects in a hypothetical scenario where all subjects have taken complete dose. - In this case, the data from a period in which an incomplete dose is taken would be considered as missing at random and excluded from analyses. - If the drug formulation is changed in the future studies, this estimate will provide the true relationship between the actual dose intake and its exposure under this strategy. 
Supplementary analysis
 
 - The strategy will be a Treatment policy strategy, where we are interested in the treatment effects regardless of the actual amount of dose taken. - The analysis will include PK parameters derived based on concentrations of both complete and partial doses (if data permits based on criteria described in Section 8.1.1.2) and will be analysed using the nominal or prescribed dose. - If the drug formulation remains unchanged in the future studies, this estimate will provide the true relationship between a nominal dose and its exposure under this strategy, i.e., in a close to real-world setting
Subject drops out	Related to treatment/	
 - The primary strategy will be a Hypothetical strategy, where we are interested in the

due to Adverse events	If the adverse event is confirmed to be related to study treatment	treatment effects in a hypothetical scenario where discontinuation due to an AE would not happen. 
 - The missing data after discontinuation will be assumed to be missing at random - The derived PK parameters of the last fully or partially completed period will be calculated if data permits (See section 8.1.1.2 Derived Pharmacokinetic Parameters for details on derivation criteria).
-----------------------	--	--

8.3.5. Statistical Analyses / Methods

Details of the planned displays are provided in **Error! Reference source not found.**: List of Data Displays and will be based on GSK Data Standards and statistical principles. Graphical presentations will be provided if appropriate. All data will be listed.

8.3.5.1. Statistical Methodology Specification

The following statistical analyses will only be performed if sufficient data is available (i.e. if subjects have well defined plasma profiles).

Pharmacokinetic analysis will be the responsibility of the Clinical Pharmacology Modelling and Simulation Department, (CPMS) and Statistical analyses of the pharmacokinetic parameters will be the responsibility of the Biostatistics Department.

(2) Statistical analysis for dose proportionality – Single and Repeat dose study parts	
Endpoint / Variables	

 For SAD part: AUC(0-∞), Cmax For MAD part: AUC(0-tau), Cmax, Ct_{tau} 	
Model Specification	

 Power model $y = \alpha * dose^\beta$ 
where y denotes the PK parameter being analyzed, dose denotes the total dose administered to a subject. The α denotes random subject effect in the repeat dose Part B. In the crossover single ascending dose Part A, alpha depends upon random subject effect and period effect.
 Log_e transformed data will be analysed by fitting the following terms in the mixed effect model: 
 Fixed effect: log_e (dose), period (period will be included in SAD part only) Random effect: Subject Data from all available doses in each part of the study will be considered (as described in Section 8.1.1.2). 	

• An unstructured covariance structure will be considered for the G matrix describing the between subject variability.• Based on the intercurrent events observed in the study, appropriate strategies from Table 4 in Section 8.3.4 will be considered for handling of missing data (if any) and interpretation of the analysis results. If multiple intercurrent events are observed (for e.g., if the subject does not take the full treatment as well he withdraws study consent), then the data will be handled using more than one strategy as described in Table 4 and interpretations of the results will be made accordingly.
Model Checking & Diagnostics

• For the Mixed Model, model assumptions will be checked, and appropriate adjustments may be applied based on the data.• Distributional assumptions underlying the model used for analysis will be examined by obtaining a normal probability plot of the residuals and a plot of the residuals versus the fitted values (i.e., checking the normality assumption and constant variance assumption of the model respectively) to gain confidence that the model assumptions are reasonable.• If there are any departures from the distributional assumptions, alternative transformations, such as data squared or square root of data, will be explored.• Non-parametric analyses will be conducted if the normality assumption does not hold for any of the alternative transformations.
Model Results Presentation

• Estimates of the mean slopes of $\log_e(\text{dose})$ will be reported along with corresponding 90% confidence intervals (slope ≈ 1 implied dose proportionality).

8.4. Statistical analysis for dose accumulation – Repeat dose study part

8.4.1. Endpoints/Variables

To assess the dose accumulation, the statistical analysis will be based on the ratios of RAUC(0-tau), RCmax and RCtau respectively.

8.4.2. Summary Measure

The summary measure will be the point estimates and 90% CIs of mean differences of 'Day 10 – Day 1' based on the log-transformed data and after back-transformation of this estimated differences, the geometric means of the ratio 'Day 10: Day 1' will be presented.

8.4.3. Population of Interest

These analyses will be based on the PK population.

8.4.4. Strategy for Intercurrent (Post-Randomization) Events

In the Table 5 below, the possible intercurrent events and the rationale for relating them to treatment or otherwise is described. Once a subject discontinues from study treatment, they will proceed straight to follow up and no further data will be collected.

All subjects' data will be included in data listings irrespective of the strategies followed for the analysis.

If feasible, subjects will be replaced until the desired sample size is attained.

Table 5 Strategies for Intercurrent events

Intercurrent events	Relation to treatment and rationale	Strategy, rationale and details of action taken
Subject withdraws study consent	
Not related to treatment/
 
Subject drops out due to logistic reasons and not due to any event related to treatment
	
 - The strategy will be a While-on-Treatment strategy, where we are interested in the treatment effects prior to the withdrawal only. - Subjects' data available up to the withdrawal will be included in the dose accumulation analyses. - If a subject withdraws consent during a period, the missing data post withdrawal will not be imputed. - The derived PK parameters for e.g., AUC, C_{max} etc. of that partially completed period will be calculated if data permits (See section

		8.1.1.2 Derived Pharmacokinetic Parameters for details on derivation criteria).
Subject does not take the full treatment	
Not related to treatment/
 
The treatment will be administered as a powder dissolved in diluent. To ensure all treatment is ingested, the bottle containing the dispersion will be rinsed three times and the subject will be expected to ingest this in addition to the initial dispersion. If three rinses are not all ingested, the subject may not take the full treatment dose.
	
In the current formulation, it is hard to measure the exact proportion of dose ingested if not all rinses are taken. It is also uncertain whether the formulation could change in future development. To account for this, we propose two different strategies described below. If this intercurrent event is not observed, then both strategies will provide the same results and only the hypothetical strategy will be presented for the final analysis.
 
Primary analysis
 
 - The strategy will be a Hypothetical strategy, where we are interested in the treatment effects in a hypothetical scenario where all subjects have taken complete dose. - In this case, the data from a period in which an incomplete dose is taken would be considered as missing at random and excluded from analyses. - If the drug formulation is changed in the future studies, this estimate will provide the true relationship between the actual dose intake and its exposure under this strategy. 
Supplementary analysis
 
 - The strategy will be a Treatment policy strategy, where we are interested in the treatment effects regardless of the actual amount of dose taken. - The analysis will include PK parameters derived based on concentrations of both complete and partial doses (if data permits based on criteria described in Section 8.1.1.2) and will be analysed using the nominal or prescribed dose. - If the drug formulation remains unchanged in the future studies, this estimate will provide the true relationship between a nominal dose and its exposure under this strategy, i.e., close to a real-world setting.
Subject drops out	Related to treatment/	
 - The primary strategy will be a Hypothetical strategy, where we are interested in the

due to Adverse events	If the adverse event is confirmed to be related to study treatment	treatment effects in a hypothetical scenario where discontinuation due to an AE would not happen. 
 - The missing data after discontinuation will be assumed to be missing at random - The derived PK parameters of the last fully or partially completed period will be calculated if data permits (See section 8.1.1.2 Derived Pharmacokinetic Parameters for details on derivation criteria).
-----------------------	--	--

8.4.5. Statistical Analyses / Methods

Details of the planned displays are provided in **Error! Reference source not found.**: List of Data Displays and will be based on GSK Data Standards and statistical principles. Graphical presentations will be provided if appropriate. All data will be listed.

8.4.5.1. Statistical Methodology Specification

The following statistical analyses will only be performed if sufficient data is available (i.e. if subjects have well defined plasma profiles).

Pharmacokinetic analysis will be the responsibility of the Clinical Pharmacology Modelling and Simulation Department, (CPMS) and Statistical analyses of the pharmacokinetic parameters will be the responsibility of the Biostatistics Department.

Statistical analysis for dose accumulation – Repeat dose study part	
Endpoint / Variables	

 • RAUC(0-tau) • RCmax • RCtau 	
Model Specification	

 • Will be statistically analysed using a mixed model (MM) using a \log_e-transformation. The mixed model will contain: 
 ○ Fixed effects: dose, day and dose*day ○ Random effect: Subject 	

Here dose denotes the total dose administered per day to a subject.
 
 • The Kenward and Roger method for approximating the denominator degrees of freedom and correcting for bias in the estimated variance-covariance of the fixed effects will be used. • An unstructured type of the covariance matrices R (accounting for the within subject variability) and G (accounting for the between subject variability) will be used. • Based on the intercurrent events observed in the study, appropriate strategies from Table 5 in Section 8.4.4 will be considered for handling of missing data (if any) and interpretation of the analysis results. If multiple intercurrent events are observed (for e.g., if the subject does 	

not take the full treatment as well he withdraws study consent), then the data will be handled using more than one strategy as described in Table 5 and interpretations of the results will be made accordingly.
Model Checking & Diagnostics 
For the Mixed Model, model assumptions will be checked, and appropriate adjustments may be applied based on the data.Distributional assumptions underlying the model used for analysis will be examined by obtaining a normal probability plot of the residuals and a plot of the residuals versus the fitted values (i.e. checking the normality assumption and constant variance assumption of the model respectively) to gain confidence that the model assumptions are reasonable.If there are any departures from the distributional assumptions, alternative transformations, such as data squared or square root of data, will be explored.Non-parametric analyses will be conducted if the normality assumption does not hold for any of the alternative transformations.If this model fails to converge, alternative covariance structures may be considered in the following order (1) Compound Symmetry (CS) and (2) Variance Components (VC).
Model Results Presentation 
For each dose, point estimates and 90% confidence intervals for the differences "Day 10 - Day 1" will be presented based on the log-transformed data.These point estimates and associated 90% confidence intervals will then be exponentially back-transformed to provide point and 90% confidence interval estimates for the ratios "Day 10: Day 1" for each active dose.If both the dose and day by dose interaction terms are not significant, and only day effect is significant based on the data, then to evaluate the effect of day, a single point estimate and confidence interval pooled across all doses by day will be constructed.

8.5. Statistical analysis for time invariance ratio of GSK3186899 – Repeat dose study part

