**Table 3 Predicted human blood PK parameters for GSK3186899 that were employed for simulation of human PK profile**

Parameter	Predicted Value	%CV #
Clearance (mL/hr/kg)	438	50
Vdss (mL/kg)	800	30
KA (hr-1)	0.7	10
F (%)	50	NA

[figure not shown]
# assumed variability for human PK simulation; NA not applicable

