#### **5.5.2. Maximum SAD Dose Determination**

A nominal maximum SAD dose of 2500mg is proposed for this study to achieve  $>$ target plasma  $AUC_{0-24h}$  for maximum pharmacology. This is based on the consideration that if a dose-dependent bioavailability decrease is observed as per the simulations presented, then a nominal dose of 1200 mg BID will be anticipated to produce desired therapeutic effect. If 1200 mg BID is ATD, then to support this dose in multiple ascending dose (MAD) study, exposures coverage from nominal SAD dose is desired. Hence, a maximum nominal SAD dose of 2500 mg is considered in this FTIH to support the development of GSK3186899. Accumulation following repeat dosing is not evident from simulations. The exposures from this dose have several-fold margins to the NOAELs from female rat (with dose independent F: 3-fold for Cmax & 7-fold for  $AUC_{0-24h}$ ; with dose dependent F: 7-fold for Cmax & 14-fold for  $AUC_{0-24h}$ ). The nonclinical data support the conduct of clinical studies in healthy volunteers up to 3 weeks duration up to 3-fold below the mean systemic exposure at the female NOAEL of 100 mg/kg/day in the rat 4-week study (AUC: 434  $\mu\text{g.h/mL}$ , Cmax: 46.2  $\mu\text{g/mL}$ ) with appropriate monitoring in place. The dose escalation will proceed up to nominal top dose of 2500 mg in dose independent F scenario to provided PK stopping criteria is not met; considering the PKPD variability and translational uncertainty of the preclinical data to provide flexible dosing regimen option.

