	
to assess attainment of steady state.
 
To estimate the extent of accumulation after repeat dosing, the observed accumulation ratio for AUC (<math>(\text{RAUC}_{(0-\text{tau})})</math>), <math>C_{\max}</math> (<math>\text{RC}_{\max}</math>) and <math>C_{\text{tau}}</math> (<math>\text{RC}_{\text{tau}}</math>) may be determined.
 
Statistical analyses of the pharmacokinetic parameter data will be the responsibility of Biostatistics, GlaxoSmithKline. No formal hypotheses will be tested. Pharmacokinetic data will be presented in graphical and/or tabular form and will be summarized descriptively. Full details on the statistical aspects will be detailed in the Reporting and Analysis Plan (RAP).
 
Food Effect (SAD part)
 
The effect of food on the pharmacokinetics of GSK3186899 will be examined. <math>AUC(0-t)</math>, <math>AUC(0-\infty)</math> and <math>C_{\max}</math> of GSK3186899 will be analyzed after a <math>\log_e</math>-transformation of the data. An analysis of variance model will be fitted along with 90% confidence intervals using a mixed effects model, with fed/fasted condition as a fixed effect and subject as a random effect. Point estimates and corresponding 90% confidence intervals will be constructed for the comparisons of interest of GSK3186899 fed – GSK3186899 fasted, using the residual variance. These will then be back-transformed to provide point estimates and corresponding 90% confidence intervals for the geometric mean ratios fed: fasted.
 
Dose Proportionality (SAD and MAD parts)
 
Dose proportionality will be assessed following single doses of GSK3186899 (SAD part) via analyses of <math>AUC(0-\infty)</math> and <math>C_{\max}</math>.
 
Dose proportionality following repeated dosing (MAD part) will be assessed using <math>AUC(0-\text{tau})</math>, <math>C_{\max}</math> and <math>C_{\text{tau}}</math>.
 
A statistical analysis will be performed using the power model. The analysis will be performed on <math>\log_e</math>-transformed data. For each of these parameters a mixed effects model will be fitted with <math>\log_e</math> (dose) as a fixed effect and individual subject fitted as random effects. Estimates of the mean slopes of <math>\log_e</math> (dose) will be reported along with corresponding 90% confidence intervals (slope <math>\approx 1</math> implies dose proportionality).
 
Accumulation (MAD part)
 
The extent of accumulation of GSK3186899 will be based on AUC (<math>\text{RAUC}_{(0-\text{tau})}</math>), <math>C_{\max}</math> (<math>\text{RC}_{\max}</math>) and <math>C_{\text{tau}}</math> (<math>\text{RC}_{\text{tau}}</math>).
 
The focus of the statistical analysis will be to estimate the accumulation ratio, <math>R_o</math>, on the pharmacokinetics of GSK3186899. Following <math>\log_e</math>-transformation, <math>AUC(0-\text{tau})</math> on Day 1 and <math>AUC(0-\text{tau})</math> on the day of last dose will be analysed by a mixed

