
Endpoint	Statistical Analysis Methods
	
effect model, fitting fixed effect terms for dose, day, and day by dose interaction, and fitting subject as a random effect.
 
For each dose, point estimates and 90% confidence intervals for the differences "Day 10 - Day 1" will be constructed using the appropriate error term. The point estimates and associated 90% confidence intervals will then be exponentially back-transformed to provide point and 90% confidence interval estimates for the ratios "Day 10: Day 1" for each active dose. If both the dose and day by dose interaction terms are not significant, a single point estimate and confidence interval pooled across all doses will also be constructed.
 
<math>RC_{max}</math> and <math>RC_{tau}</math> will be estimated in a similar approach.

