2. SUMMARY OF KEY PROTOCOL INFORMATION

2.1. Changes to the Protocol Defined Statistical Analysis Plan

There were no major changes or deviations to the originally planned statistical analysis specified in the Original Protocol 208436 (Dated: 09-Jan-2019) and the Amendment 01 (Dated: 19-Mar-2019).

A minor change is made to the first secondary objective where trough plasma concentration (C_{tau}) is removed from the SAD part and added to the MAD part after confirmation from the Study Pharmacokineticist.

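### The SAP shows the pooled Day 10:Day 1 accumulation ratio only if the day effect is significant, an undeclared addition to the protocol that almost always suppresses a pooled finding of no accumulation

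*SAP*

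**What the plan says.** Protocol 10.5.2 (Accumulation) models log AUC(0-tau) on Day 1 and on the last dosing day, with dose, day and their interaction as fixed effects and subject as random. It gives a Day 10:Day 1 ratio with 90% CI for each dose, and then a pooled result: "If both the dose and day by dose interaction terms are not significant, a single point estimate and confidence interval pooled across all doses" is also to be constructed. RCmax and RCtau are treated in the same way. There is no condition on the day effect.

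SAP 8.4.5.1 keeps the model and the per-dose ratios but changes the trigger for pooling: "If both the dose and day by dose interaction terms are not significant, and only day effect is significant based on the data". Only then, it says, "a single point estimate and confidence interval pooled across all doses by day will be constructed". That last phrase does not say whether a ratio or day means are meant; it is read here as the ratio, as in the protocol.

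SAP 2.1 states: "There were no major changes or deviations to the originally planned statistical analysis specified in the Original Protocol 208436". The one minor change it records begins "A minor change is made to the first secondary objective where trough plasma concentration" and concerns moving Ctau from the SAD part to the MAD part. Neither document gives a significance level for these model terms.

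The result expected before the study is in Protocol 5.5.2: "Accumulation following repeat dosing is not evident from simulations". The Table 4.10 shell reads a ratio of 1 as no accumulation and has per-dose rows only.

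**The concern.** There are two separate points.

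**The day condition, new in the SAP.** In this model the day contrast averaged over doses is the log of the pooled Day 10:Day 1 ratio. Testing day is therefore testing whether the pooled ratio equals 1, and the quantity is reported only when its own test rejects. A pooled result compatible with no accumulation, which the protocol expects, goes untabulated. Any pooled value that does appear has been selected for its distance from 1.

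**The dose condition, carried over from the protocol.** Exposure is not dose-normalised, so a dose main effect says only that higher doses give higher exposure. Whether one ratio fits all doses is a matter for dose-by-day alone.

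At stake is the most precise summary for a secondary objective, mainly for RCmax and RCtau, in a study that sets out to estimate rather than to test.

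**Working it through.** Neither document gives a power or probability for this analysis, so there is no figure to reproduce.

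**1. Why a shown CI cannot include 1.** Let D be the pooled log ratio, from 3 × 6 = 18 active participants, with 15 df. The 90% CI is D ± t(0.95, 15)·SE. Day is significant when |D| > t(1 − α/2, 15)·SE. For α ≤ 10% that multiplier is at least 1.753, the one used in the CI, so the CI excludes 0 whenever day is significant. If the pooled CI is instead refitted without dose terms (17 df), 0% of shown CIs include 1 at α = 5% and about 3% at α = 10%.

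**2. How far from 1 the estimate must be.** SE = s_w·√(2/18), with s_w = √ln(1 + CVw²).
- AUC, CVw 20%: s_w = 0.198, SE = 0.066. The 90% CI is the estimate ×/÷ exp(1.753 × 0.066) = 1.12. At α = 5% the multiplier is 2.131, so the estimate must lie above about 1.15 or below about 0.87.
- Cmax, CVw 30%: s_w = 0.294, SE = 0.098. The CI is ×/÷ 1.19, and the limits at α = 5% are about 1.23 and 0.81.

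**3. Expected ratio.** With the stated half-life of 1.3 h and a 12 h interval, 1/(1 − exp(−(ln 2/1.3) × 12)) = 1.002. Averaging over the variability in protocol Table 3 gives geometric means of 1.025 (RAUC), 1.025 (RCmax) and 1.015 (RCtau).

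**4. Simulation inputs.**
- Six active per cohort (SAP 2.3), at 0.5X, 0.75X and X (Protocol 5.5.5).
- CVw 20% for AUC and 30% for Cmax, from Protocol 10.2. These are given for the food-effect cohort and assumed to hold in Part B. For Ctau no document gives a CVw; 30% is assumed.
- Between-subject spread from Table 3 (CL 50%, Vdss 30%, KA 10%; there labelled "assumed variability for human PK simulation") through a one-compartment oral model: log SD 0.444 for AUC(0-12) (CV 47%), 0.275 for Cmax (CV 28%) and 1.80 for the 12 h concentration.
- Dose means either proportional, or following the protocol's dose-dependent F = 0.5 − 0.3·dose/(300 + dose) with X = 600 or 1200 mg.
- α of 5% and 10%, both assumed.
- Tests: dose F(2,15), dose-by-day F(2,15), day t(15). 100,000 trials per setting.

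**5. Share of trials with the pooled row shown, true ratio 1.0** (ranges span the two α levels)

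| Parameter | PK | SAP rule | Protocol rule | Blocked by dose condition alone |
|---|---|---|---|---|
| AUC | proportional | 2.0-2.7% | 29-43% | 55-68% |
| AUC | dose-dependent F | 2.9-4.4% | 45-61% | 35-51% |
| Cmax | proportional | 0.9% | 9-18% | 81-90% |
| Cmax | dose-dependent F | 1.8-2.3% | 24-39% | 59-74% |
| Ctau | both | 4.1-7.4% | 77-89% | 7-14% |

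Conditioning on dose-by-day alone would show the row in 90-95%. Of the 90% CIs shown, 0% include 1 under the SAP rule and about 90% under the protocol rule.

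**6. True ratios other than 1, SAP rule**

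| Parameter | True ratio | Shown in | Average shown value | 90% CI covers truth when shown |
|---|---|---|---|---|
| AUC | 1.025 | 2.6-5.3% | 1.09-1.11 | 7-41% |
| Cmax | 1.025 | 1.0-2.6% | 1.10-1.12 | 0-30% |
| Ctau | 1.015 | 4.3-7.7% | 1.06-1.08 | 0-17% |
| AUC | 1.1 | 11-18% | 1.17-1.19 | – |
| Cmax | 1.1 | 2-6% | 1.23-1.26 | – |
| Ctau | 1.1 | 13-18% | 1.24-1.26 | – |

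**7. Sensitivity.** Over CVb 30-50% and CVw 20-30% at ratio 1.0, the SAP rule shows the row in 0.6-3.3% (proportional) or 1.6-4.9% (dose-dependent F), and the protocol rule in 6-52% or 19-67%. For Ctau at ratio 1.015, CVw of 20% and 80% give 4.1-8.2% shown.

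**The case against.** The strongest reply is that little is lost.

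- **Per-dose ratios with 90% CIs are always tabulated.** SAP 8.5 also gives an all-dose AUC ratio without this gate, if Day 1 AUC(0-∞) is estimable, and Listings 73 and 79 hold the derived parameters and raw model output. This stands and limits the harm. It does not replace a pooled RCmax or RCtau. At CVw 20%, a per-dose CI from 6 participants (5 df) is ×/÷ about 1.26, against 1.12 pooled.
- **The SAP rule adds no misleading pooled CIs.** Its rows are a subset of the protocol's. At ratio 1.0 and α = 5%, trials showing a pooled CI that misses the truth are 2.1% against 4.2% (AUC), 0.9% against 1.7% (Cmax) and 4.2% against 8.5% (Ctau). This stands. The low coverage above is conditional on the row being shown, and the main loss is the missing row.
- **The gate is two-sided.** At a true ratio of 1, about half the shown values fall below 1. This also stands: the rule favours any departure from 1, not accumulation specifically.
- **For AUC and Cmax the inherited dose condition blocks more trials than the day condition.** True where PK is proportional, so restoring the protocol rule still leaves Cmax mostly untabulated. For Ctau the day condition is the main obstacle.
- **Some scenarios are weakly supported.** The SAP records that the top single dose was dropped for higher than expected exposure, which fits poorly with falling bioavailability, and the Ctau runs ignore non-quantifiable troughs. The proportional AUC and Cmax results depend on neither.
- **The protocol leaves statistical detail to the analysis plan.** It had, however, already fixed when the pooled ratio is constructed. Narrowing that trigger is a change and belongs in SAP 2.1, even as a minor one.

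**Conclusion.** The concern holds. The SAP adds a condition that the protocol does not have and does not declare it. At any significance level up to 10%, a pooled 90% CI from the same model that includes 1 can never be shown; this follows from the algebra and needs no simulation. If there is no accumulation, the pooled row appears in roughly 1-7% of trials across the three parameters, against 9-89% under the protocol rule. If the true ratio is 1.1, values that reach the table average 1.17-1.26.

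The percentages rest on assumed significance levels, on food-effect CVw values carried into Part B, on Table 3 variability, and on an assumed CVw for Ctau. The direction depends on none of these. The matter is a secondary PK summary that no decision rule uses, so it should be corrected but does not threaten the study's conclusions.

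**What to change.** **Minimum.** In SAP 8.4.5.1, delete the clause requiring a significant day effect and the words *by day*, say explicitly that the pooled quantity is the Day 10:Day 1 ratio with its 90% CI, and state the significance level for the remaining tests. This restores the protocol rule, so SAP 2.1 needs no entry.

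**Preferred.** For RAUC(0-tau), RCmax and RCtau, present one Day 10:Day 1 ratio with 90% CI averaged over doses beside the per-dose ratios, whatever the significance of any model term, or conditional on dose-by-day alone at a stated level. Add an all-doses row to the Table 4.10 shell, and record in SAP 2.1 that the protocol's dose condition has been dropped. This also resolves the Cmax problem, which the minimum change does not.

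**Cost.** The minimum is a short edit to one sentence. The preferred version is one SAP sentence, one shell row and one line in SAP 2.1, with no new data or model. Its drawback is that the pooled row becomes an average if accumulation differs by dose; the per-dose rows next to it would show that.
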